#### **7.1.7 Safety Laboratory Measurements**

No scheduled safety laboratory measurements are planned for this study.

### **7.2 Efficacy Assessment**

There is no assessment of efficacy in this study.

## 7.3 Immunogenicity Assessment

The measures of immunogenicity used in this study are standard, i.e., widely used and generally recognized as reliable, accurate, and relevant (able to describe the quality and extent of the immune response).

The immunogenicity analysis will evaluate the immunogenicity of the study vaccine, which will be measured by the HI and MN assay by titrating antibodies against the homologous influenza strains.

For the primary immunogenicity objectives, HI antibody responses using a cell-derived target virus will be evaluated for all strains. In case of a lack of agglutination for a specific strain using HI assay, immunogenicity for that strain will be assessed as measured by the MN assay.

For the secondary immunogenicity objectives, HI and MN antibody responses using cell-derived target virus will be evaluated for all strains. In case of a lack of agglutination for a specific strain using HI assay, immunogenicity for that strain will be assessed as measured by the MN assay.

For the exploratory immunogenicity evaluation, HI antibody responses may be evaluated for all strain using egg-derived target viruses.

Testing will be conducted by the Sponsor or designated laboratory in a blinded manner towards the treatment arm.

## 8 STATISTICAL CONSIDERATIONS

A complete description of the statistical analyses and methods will be available in the Statistical Analysis Plan, which will be finalized before the database is locked for the primary analysis. The primary analysis will be conducted on the immunogenicity and safety data collected up to Day 29.

### 8.1 Endpoints

#### 8.1.1 Primary Endpoint(s)

The primary objective of the study is to assess the immunogenicity of aQIVc compared to QIVc, aQIV, and QIVr as measured by HI assay using *cell-derived* target viruses. The primary endpoints are therefore the set of immunogenicity endpoints routinely applied for studies with such objectives.

### 8.1.1.1 Primary Immunogenicity Endpoints

Humoral immune response in terms of HI antibody response against homologous *cell-derived* vaccine strains (A/H1N1, A/H3N2, B/Yamagata and B/Victoria):

- Geometric Mean Titer (GMT): Geometric mean of HI antibodies at Day 29;
- Geometric Mean Fold Increase (GMFI): The Geometric mean of the fold increase in serum HI GMTs post-vaccination (Day 29) compared to pre-vaccination (Day 1);
- Percentages of subjects with HI titers  $\geq 1:40$  at Day 29;
- Percentage of subjects with seroconversion (defined as a  $\geq 4$ -fold increase in titer post-vaccination in those with pre-vaccination titer above the LLOQ (1:10), or a post-vaccination titer  $\geq 1:40$  for subjects with baseline titer below the LLOQ (1:10) for HI antibodies at Day 29).

Note that the HI assay could be replaced by the MN assay due to a lack of agglutination.

### 8.1.1.2 Primary Safety Endpoints

No primary safety endpoints have been defined.

## 8.1.2 Secondary Endpoints

Secondary endpoints assessed in the study include the safety endpoints of solicited and unsolicited adverse events, the immunogenicity endpoints measured by the HI assay assessed at Day 181 and in addition the immunogenicity endpoints measured by the MN assay both at Day 29 and day 181.

### 8.1.2.1 Secondary Safety Endpoints

The secondary safety endpoints include the proportion of subjects reporting solicited and unsolicited adverse events:

- Percentage of subjects reporting a local and/or systemic adverse event for the 7 days following the vaccination (Day 1 to Day 7)
- Percentage of subjects reporting unsolicited adverse events for 28 days following vaccination (Day 1 to Day 29).
- Percentage of subjects reporting serious AEs, MA AEs, AEs leading to withdrawal or AESIs as collected during the study (Day 1 to End of Study).

### 8.1.2.2 Secondary Immunogenicity Endpoints

Humoral immune response in terms of HI antibody response against homologous *cell-derived* vaccine strains (A/H1N1, A/H3N2, B/Yamagata and B/Victoria) at Day 181:

- GMT: Geometric mean of HI antibodies at Day 181;
- GMFI: The Geometric mean of the fold increase in serum HI GMTs post-vaccination (Day 181) compared to pre-vaccination (Day 1);
- Percentages of subjects with HI titers  $\geq 1:40$  on Day 181.

In addition, the humoral immune response in terms of MN antibody response against homologous *cell-derived* vaccine strains (A/H1N1, A/H3N2, B/Yamagata and B/Victoria) at Days 29 and 181:

- GMT: Geometric mean of MN antibodies at Days 29 and 181;
- GMFI: The Geometric mean of the fold increase in serum MN GMTs post-vaccination (Day 29 and Day 181) compared to pre-vaccination (Day 1);
- Percentages of subjects with seroconversion (defined as  $\geq 4$ -fold increase for subjects with pre-vaccination MN titers  $\geq$  Lower Limit of Quantitation (LLOQ) or as  $\geq 4$ LLOQ for subjects with pre-vaccination MN titer <LLOQ) at Day 29.

### 8.1.3 Exploratory Endpoints

Exploratory endpoints that may be assessed in the study include the immunogenicity endpoints as measured by HI assay using *egg-derived* target viruses on Day 29, 28 days after vaccination. Refer to the SAP for more details.

#### 8.1.3.1 Exploratory Safety Endpoints

No exploratory safety endpoints were defined.

#### 8.1.3.2 Exploratory Immunogenicity Endpoints

Humoral immune response in terms of HI antibody response against homologous *egg-derived* vaccine strains (A/H1N1, A/H3N2, B/Yamagata and B/Victoria):

- GMT: Geometric mean of HI antibodies at Day 29;
- GMFI: The Geometric mean of the fold increase in serum HI GMTs post-vaccination (Day 29) compared to pre-vaccination (Day 1);
- Percentages of subjects with HI titers  $\geq 1:40$  at Day 29;

- Percentage of subjects with seroconversion for HI antibodies on Day 29.

The results of these exploratory analyses may be presented in an addendum to the Clinical Study Report (CSR)

## 8.2 Success Criteria

This study is a Phase 2 study to explore the immunogenicity of aQIVc versus comparator vaccines (QIVc, aQIV, and QIVr). No success criteria are pre-specified.

## 8.3 Analysis Sets

### 8.3.1 All Enrolled Set

All screened subjects who provide informed consent, receive a subject ID and provide demographic and/or baseline screening assessments, regardless of the subject's randomization and treatment status in the study

### 8.3.2 All Exposed Set

All subjects in the All Enrolled Set who are randomized and received study vaccination.

### 8.3.3 Safety Set

#### Solicited Safety Set

All subjects in the Exposed Set with any solicited adverse event data including temperature measurements or use of analgesics/antipyretics.

#### Unsolicited Safety Set (unsolicited adverse events)

All subjects in the Exposed Set with unsolicited adverse event data.

#### Overall Safety Set

All subjects who are in the Solicited Safety Set or in the Unsolicited Safety Set.

Subjects will be analyzed as "treated" (i.e., according to the vaccine a subject received, rather than the vaccine to which the subject may have been randomized).

### 8.3.4 Full Analysis Set (FAS) Immunogenicity

#### Full Analysis Set Immunogenicity

All subjects in the All Enrolled Set who are randomized, received study vaccination and provided immunogenicity data on Day 1 and Day 29 assessment.

In case of vaccination error, subjects in the FAS sets will be analyzed “as-treated” (i.e., according to the vaccine the subject actually received).

### 8.3.5 Per Protocol Set (PPS) Immunogenicity

All subjects in the FAS Immunogenicity who:

- Correctly receive the vaccine (i.e., receive the vaccine to which the subject is randomized and at the scheduled time point).
- Have no protocol deviations leading to exclusion (see [Section 8.3.8](#), Protocol Deviations) as defined prior to unblinding / analysis.
- Are not excluded due to other reasons defined prior to unblinding or analysis, including subjects who withdrew informed consent prior to Day 28.

### 8.3.6 Other Analysis Sets

Not applicable

### 8.3.7 Subgroups

Primary and secondary analyses of immunogenicity and safety endpoints will be done for the total population and by age subgroup (50 – 64 years and  $\geq$  65 years).

Additional subgroup analysis will be conducted for previous vaccination history. Refer to the SAP for further details.

### 8.3.8 Protocol Deviations

A protocol deviation is any change, divergence, or departure from the study design or procedures of a study protocol. A protocol deviation may be a reason to remove data from an analysis set at the time of analysis. CSR-reportable protocol deviations will be defined as exclusionary from the analysis according to protocol objectives and endpoints, which will be specified in the statistical

analysis plan. In some cases, exclusion of data may be due to a reason other than a protocol deviation, e.g. early termination.

## 8.4 Statistical Analysis Plan

### 8.4.1 Analysis of Demographic and Baseline Characteristics

Descriptive statistics (mean, standard deviation, median, minimum and maximum) for age, height, weight, BMI and comorbidity score at enrolment will be calculated overall and by vaccine group.

Distributions of subjects by sex, race and ethnic origin, prior vaccination status and site will be summarized overall and by vaccine group.

Demographic and baseline characteristics will also be presented by the age subgroup.

### 8.4.2 Analysis of Primary Objectives

#### 8.4.2.1 Analysis of Primary Safety Objectives

Not applicable.

#### 8.4.2.2 Analysis of Primary Immunogenicity Objectives

The primary objective is to assess the immunogenicity assessed using the HI assay at Day 29.

##### 8.4.2.2.1 Statistical Hypothesis

No statistical testing will be performed for the immunogenicity objectives.

##### 8.4.2.2.2 Analysis Sets

All immunogenicity objectives will be evaluated based on the PPS Immunogenicity. Only in case, more than 5% of subjects are excluded, additional analysis based on the FAS Immunogenicity will be conducted.

##### 8.4.2.2.3 Statistical Methods

All statistical analyses for HI (and MN) titers will be performed on the logarithmically (base 10) transformed values. Individual HI titers below the detection limit (<10) will be set to half of that limit (5); values above the upper limit of quantification will be set to the upper limit.

Print Date (Local): 30-mrt-2020 10:41:00

Reverse cumulative distribution curves will be derived by time-point and strain.

Crude estimates for GMTs, GMFIs and pertaining 2-sided 95% CIs will be calculated assuming a log-normal distribution of the titers and will be completed by providing minimum, maximum and median titers for each vaccine group. Binary data (i.e., percentages of subjects with seroconversion and with titer  $\geq 1:40$ ) will be summarized for each group using crude estimates and will be reported together with 2-sided 95% CIs calculated according to Clopper Pearson's method. No multiplicity adjustment to the CI levels will be implemented.

For immunogenicity data, it may be reasonable to consider missing immunogenicity values as missing completely at random (MCAR), i.e., not informative. Therefore, the immunogenicity analysis will comprise a complete case analysis only, without introducing any bias.

The analysis model for the HI GMT will be done using a general linear model on log-transformed (base 10) Day 29 titers as the outcome variable and as covariates: treatment groups (aQIVc, QIVc, aQIV, and QIVr), pre-vaccination titer, age stratum. From this model, adjusted differences in the least square means (on the log scale) will be produced with 95% confidence limits for aQIVc versus QIVc, for aQIVc versus aQIV and for aQIVc versus QIVr. The estimated difference and the confidence limits will be back-transformed to obtain an *adjusted GMT ratio* with 95% confidence limits. Each of the four strains will be analyzed separately.

Potential interaction between age stratum and treatment effect will be examined, as well as the other co-variates such as previous vaccination history and age were taken as a continuous factor.

A similar model will be used for the GMFI on Day 29.

The binary endpoints (i.e. seroconversion or titer  $\geq 1:40$ ) will be compared using the Miettinen and Nurminen method without adjustment for the age stratum. The results will be presented as the difference in the percentage of subjects with 95% confidence intervals. Additional supportive analyses will be done using generalized linear models with factors for vaccine group, age subgroup, pre-vaccination titer as well as history of vaccination. Adjusted differences between vaccine groups with 2-sided 95% CI will be calculated based on the model and potential interaction effects will be examined.

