Vaccination is the primary method for preventing influenza and its severe complications. The efficacy of the conventional influenza vaccines in the adult population is demonstrated to be high (Roshini and Miller 2019). In contrast, the efficacy in elderly individuals is significantly lower due to the aging of the immune system (ie immunosenescence) and underlying medical conditions that can both

increase the risk of influenza complications as well as interfere with immune responses ([Sasaki et al. 2011](#)).

In view of the limitations of conventional influenza vaccines in older adults, there continues to be an unmet need for a new generation of influenza vaccines that provides more consistent and broader coverage against all seasonal virus subtypes and variants ([Wong and Webby 2013](#); [Reber et al. 2012](#)).

One approach to overcoming immunosenescence is to enhance the immune response by the addition of an adjuvant, such as the squalene and water emulsion adjuvant, MF59. The addition of MF59 increases antigen uptake, macrophage recruitment, macrophage migration, and the spectrum of antibody recognition of HA epitopes ([Calabro et al. 2011](#); [O'Hagan et al. 2012](#)). Thus, when added to influenza vaccines, MF59 increases vaccine immunogenicity against both homologous and heterologous strains. Fluad®, Seqirus's trivalent seasonal influenza egg-based vaccine adjuvanted with MF59, has been licensed for use in Europe since 1997 and in the US since 2015. It has been shown to generate significantly higher geometric mean hemagglutination inhibition (HI) titers and rates of seroconversion than a nonadjuvanted trivalent influenza vaccine comparator in elderly subjects ([Frey et al. 2014](#)).

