## 8.5 Sample Size and Power Considerations of Primary Objectives

This study is an exploratory Phase 2 study without any formal inferential analysis. The total sample size of 480 subjects has been determined by the feasibility of conducting the study in one season.

This sample size – including around 10% of exclusions – is enough to obtain preliminary immunogenicity data. [Table 8-1](#) illustrates the effects which can be detected depending (80% power and the two-sided significance level of 0.05) on different values for the inter-subject variation, as well as the size of the 95% two-sided confidence interval indicating the accuracy of the estimates.

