**Table 8-1: Detectable GMT ratios**

SD #	Log10 GMT Differences that can be detected	GMT ratios can be detected	95% confidence interval (times the GMT ratio)
0.45	0.172	1.49	0.76 to 1.32
0.50	0.191	1.55	0.73 to 1.36
0.55	0.211	1.62	0.71 to 1.40
0.60	0.230	1.70	0.69 to 1.45
0.65	0.250	1.77	0.67 to 1.49
0.7	0.268	1.85	0.65 to 1.54
0.75	0.287	1.94	0.63 to 1.59
0.80	0.306	2.02	0.61 to 1.64

Notes: # range of values based on studies V7P38 and V70P3. Abbreviations: GMT= geometric mean titer. SD = Standard deviation.

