5. SAMPLE SIZE AND POWER CONSIDERATIONS

This study is an exploratory Phase 2 study without any formal hypothesis testing. The total sample size of 480 subjects has been determined by the feasibility of conducting the study in one season.

This sample size of n=108 per vaccine group – assuming 10% drop-out rates – is enough to obtain preliminary immunogenicity data.

For example, assuming a SD of log10-transformed HI titres as 0.45:

16 MAR 2021 Final Version 2.0

- In pairwise dose-group comparisons with n=108 per dose group it would be feasible to detect a difference of 1.49 in the GMT ratio with statistical power of 80% with the two sample T-test at significance level of 0.05.
- With n=108 per dose group; the precision of the GMT ratio expressed as 95% CI will be from 0.76 to 1.32 multiplied by the observed GMT estimate.

Table 2 illustrates the effects which can be detected depending (80% power and the two-sided significance level of 0.05) on different values for the inter-subject variation, as well as the size of the 95% two-sided confidence interval indicating the precision of the GMT ratio estimates.

For example, assuming a SD of log10-transformed HI titres as 0.45:

- In pairwise dose-group comparisons with n=108 per dose group it would be feasible to detect a difference of 1.49 in the GMT ratio with statistical power of 80% with the two sample T-test at significance level of 0.05.
- With n=108 per dose group; the precision of the GMT ratio expressed as 95% CI will be from 0.76 to 1.32 multiplied by the observed GMT estimate.

 Table 2 Detectable GMT ratios (80% power, 5% two-sided test)

SD #	Log10 GMT Differences that can be detected	GMT ratios can be detected	95% confidence interval (times the GMT ratio)
0.45	0.172	1.49	0.76 to 1.32
0.50	0.191	1.55	0.73 to 1.36
0.55	0.211	1.62	0.71 to 1.40
0.60	0.230	1.70	0.69 to 1.45
0.65	0.250	1.77	0.67 to 1.49
0.70	0.268	1.85	0.65 to 1.54
0.75	0.287	1.94	0.63 to 1.59
0.80	0.306	2.02	0.61 to 1.64

Notes: # range of values of the standard deviation of the log10 titers based on studies V7P38 and V70P3 (data on file). Abbreviations: GMT= geometric mean titer. SD = Standard deviation.

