The analysis model used for the comparison of the HI (or MN) GMT between aQIVc and the other three vaccine groups will be done using a general linear model on log-transformed (base 10) Day 29 titers as the outcome variable and as covariates: treatment groups (aQIVc, QIVc, aQIV, and QIVr), log-transformed pre-vaccination titer, age subgroup and previous vaccination history. From this model, adjusted differences in the least square means (on the log scale) will be produced with 95% confidence limits for aQIVc versus QIVc, for aQIVc versus aQIV and for aQIVc versus QIVr. The estimated difference and the confidence limits will be back-transformed to obtain an *adjusted GMT ratio* with 95% confidence limits. Each of the four strains will be analyzed separately.

The same analysis model, except excluding the factor age subgroup, will be run for each age subgroup separately and and present all adjusted GMT ratios with 95% confidence intervals for each age subgroup.

Additional exploratory analysis will be considered using age as continuous covariable including the assessment of interaction between age and treatment group.

Unadjusted GMT ratio will be based on a simple ANOVA model on the log-transformed titers and the treatment group.

Geometric Mean Fold Increase

Summary statistics (geometric mean, 95% confidence interval of GMT, minimum, median, maximum) of the relative increase in titers will be presented by assessment (Day 29), strain and vaccine group.

The analysis model for the fold increase in titers will be done using the same models as mentioned above on log-transformed (base 10) (Day 29 titers/Day 1 titers) as the outcome variable but excluding the log-transformed pre-vaccination titer.

16 MAR 2021 Final Version 2.0

Analysis of binary endpoints

The number and proportion of subjects achieving the binary endpoints (seroconversion or HI titer >=1:40) will be summarized by assessment (Day 29), strain and vaccine group.

For each of the influenza vaccine strains and for each of the vaccine groups, summaries will include the associated two-sided 95% confidence intervals according to Clopper-Pearson.

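### The main GMT model uses age only as 50-64 versus ≥65, and the age-subgroup models have no age term: a small loss of precision, not a bias

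*Protocol*

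**What the plan says.** The primary objective (protocol 2.1.1, SAP 2.1.1) asks for the comparison at Day 29 overall, in subjects aged 50-64 and in those aged 65 and over.

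- **Main model.** Protocol 8.4.2.2.3 fits a general linear model to log10 Day 29 titres with covariates "treatment groups (aQIVc, QIVc, aQIV, and QIVr), pre-vaccination titer, age stratum". SAP 8.1 and 11.2 use the same form and add previous vaccination history. In both documents age enters as two levels.
- **Age-subgroup models.** SAP 11.2: "The same analysis model, except excluding the factor age subgroup, will be run for each age subgroup separately". This leaves treatment, log pre-vaccination titre and vaccination history.
- **Continuous age.** After describing the model, protocol 8.4.2.2.3 says that the interaction of age stratum with treatment will be examined, along with other covariates, including age as a continuous factor. SAP 11.2 says: "Additional exploratory analysis will be considered using age as continuous covariable", and includes an age-by-treatment interaction in that analysis.
- **Age data.** SAP 8.7 defines age in whole years at Visit 1. Protocol 4.1 sets no upper age limit, and SAP 10.1 tabulates 65-74, 75-84 and 85 and over. Randomisation (protocol 5.1.4) stratifies age only at 65.
- **Age as a predictor.** SAP 8.3 names age as one of two factors that matter for the immunogenicity endpoints and gives this as the reason for including it in the model.

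**The concern.** The plan treats age as prognostic, records it in years, and then uses only one cut. Within the older stratum the model makes no distinction between a subject of 66 and one of 86. If titre varies with age inside a stratum, beyond what baseline titre and vaccination history explain, that variation stays in the residual error and widens the interval of the GMT ratio. In the subgroup models no age term remains.

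The subgroup ratios are part of the primary objective and rest on about 54 evaluable subjects per arm, so their intervals are wide. Protocol 8.5 fixes the total sample by what can be enrolled in one season, so precision cannot be gained by enrolling more. A recorded baseline covariate is a cheap source of precision. Naming it in advance also avoids a decision on age adjustment after arm imbalances have been seen.

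**Working it through.** **1. The plan's own figures.** Inputs: "80% power and the two-sided significance level of 0.05" (protocol 8.5); 108 evaluable per arm (SAP 5, 120 × 0.9); SD of log10 titre 0.45 to 0.80, described under Table 8-1 as a "range of values based on studies V7P38 and V70P3". SAP 5 states for SD 0.45 that "it would be feasible to detect a difference of 1.49 in the GMT ratio with statistical power of 80% with the two sample T-test".

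- SE = 0.45 × √(2/108) = 0.0612. Half-width = t(0.975, 214) × SE = 1.971 × 0.0612 = 0.1207. Multiplier 10^±0.1207 = 0.757 to 1.320; the SAP gives "0.76 to 1.32 multiplied by the observed GMT estimate".
- Detectable difference (noncentral t, 80% power) = 0.1723, and 10^0.1723 = 1.487 (stated 1.49).
- At SD 0.80: 0.3064, ratio 2.025, multiplier 0.610 to 1.639 (stated 0.306, 2.02, 0.61 to 1.64).

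All eight rows agree within rounding. The table rests on an unadjusted t-test, so no choice about age changes it.

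**2. Subgroup precision.** About half of each arm falls in each age group (SAP 3), so n = 108/2 = 54 per arm. At SD 0.45, SE = 0.45 × √(2/54) = 0.0866 and the 95% interval is 0.67 to 1.48 times the ratio. At SD 0.80 it is 0.50 to 2.02 times.

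**3. Gain from adding linear age.** Let r be the within-stratum partial correlation of age with log10 titre, given the other covariates. The log-scale interval shrinks by the factor √(1 − r²), and the equivalent gain in sample size is 1/(1 − r²). The documents give no value for r, so these are assumed. The upper multipliers use the normal approximation with n = 54.

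| r | Width factor | Narrower by | Equivalent n | Upper multiplier, SD 0.45 | Upper multiplier, SD 0.80 |
|---|---|---|---|---|---|
| 0 | 1.000 | 0 | 1.00 | 1.478 | 2.003 |
| 0.1 | 0.995 | 0.5% | 1.01 | 1.475 | 1.996 |
| 0.2 | 0.980 | 2.0% | 1.04 | 1.467 | 1.975 |
| 0.3 | 0.954 | 4.6% | 1.10 | 1.452 | 1.940 |

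**4. What slope each r implies.** r ≈ slope × SD(age) / SD(titre). Assume a slope of 0.01 log10 per year (in absolute value) and an age SD of 6 years, so the product is 0.06.

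- SD 0.45: r = 0.06/0.45 = 0.133, width factor 0.991, 0.9% narrower.
- SD 0.80: r = 0.06/0.80 = 0.075, width factor 0.997, 0.3% narrower.
- To reach r = 0.3 at SD 0.45 the slope must be 0.3 × 0.45/6 = 0.0225 per year, that is 10^0.225 = 1.68-fold per decade within a stratum, after adjustment for baseline titre and vaccination history.

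This uses the Table 8-1 SDs as residual SDs. The gain reaches 1% when r = √(1 − 0.99²) = 0.141, so for this slope it stays under 1% as long as the adjusted SD exceeds 0.06/0.141 = 0.43.

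**5. Chance age imbalance.** With the same slope and age SD, the SE of the difference in mean age between two arms of 54 is 6 × √(2/54) = 1.15 years. A 1-SE imbalance moves the ratio by 10^0.0115 = 1.027, and a 2-SE imbalance by 10^0.0231 = 1.055. The first shift is 0.0115/0.0866 = 13% of the subgroup SE, which already includes it.

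**6. Simulation of the subgroup model** (4 × 54 subjects, baseline titre in the model, age SD about 5, residual SD 0.45, 4,000 runs).

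| Slope, log10 per decade | Mean SE without age | Mean SE with age |
|---|---|---|
| 0.1 | 0.0872 | 0.0869 |
| 0.2 | 0.0888 | 0.0869 |
| 0.3 | 0.0912 | 0.0869 |

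Without age the mean error is about 0. Coverage, including runs with no age effect, is 94.5% to 95.4%.

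**The case against.** The plan's model is a standard choice: baseline titre plus the two stratification factors, with the reason given in SAP 8.3. A factor that is constant within a subgroup has to be dropped, and SAP 16 discloses the change. Both documents already name continuous age, and the SAP pairs it with an interaction. The study tests no hypothesis (protocol 8.4.2.2.1) and sets no success criteria (protocol 8.2), so a gain of about 1% in interval width changes no decision. All of this stands and keeps the point small. It does not put age into the adjusted ratios that will be reported for the primary objective.

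The rationale is also weaker support than it looks. The protocol's statement that "the efficacy in elderly individuals is significantly lower due to the aging of the immune system" concerns the efficacy of conventional vaccines in elderly people compared with adults, and it names underlying conditions as well. That contrast is largely what the stratum captures; it does not establish a titre slope within the older group. Protocol 1.1 also presents MF59 as a way to overcome immunosenescence, so slopes may differ by arm, and a single linear term would not show this.

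Two stronger readings are tempting. A reader might infer that chance age imbalance biases the subgroup ratios or makes their intervals too narrow. It does not: randomisation keeps the ratios unbiased, the intervals already allow for such imbalance, and the simulation shows nominal coverage. A reader might also take 4.6% as the expected gain. The documents give no age slope, and that figure needs a steep one.

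**Conclusion.** The point holds as a minor improvement in precision. Age enters the main GMT model at two levels, and the age-subgroup models have no age term. Continuous age is left to additional analyses that do not supply the reported adjusted ratios. There is no bias, no invalid interval and no change to any stated figure.

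The size rests entirely on assumed values of r, age slope and age SD. The range is about 0.5% to 4.6% of log-scale interval width for r from 0.1 to 0.3. A slope of 0.01 log10 per year with an age SD of 6 years lies at the low end, under 1% at the documents' SDs. Baseline titre and vaccination history may absorb part of any age effect, which would reduce the gain further.

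**What to change.** Before unblinding, amend protocol 8.4.2.2.3 and SAP 8.1 and 11.2:

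- Add age in years as a continuous covariate to the main GMT model and keep the age stratum.
- Add the same term to both age-subgroup models, where the age factor now drops out.
- Carry it into the Day 181 and MN models, which follow the primary methods (SAP 11.3). The GMFI models are defined by reference to the GMT models, so state whether the term applies there.
- Keep the current model as a sensitivity run, and keep the age-by-treatment interaction analysis as exploratory.

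The cost is wording, one covariate already in the database, and one degree of freedom per model. A subgroup model on 4 × 54 = 216 subjects has 216 − 6 = 210 residual degrees of freedom (intercept, three treatment contrasts, baseline titre, vaccination history) and would have 209. The term also assumes a linear age slope common to all arms, which the exploratory interaction analysis can check.
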